#### **2.2.4 Study Design**

This study is a prospective evaluation of patients receiving the investigational device to determine the proportion in whom successful implantation is achieved, as indicated by aneurysm exclusion and graft patency at implant, time of discharge, and 1-, 6-, and 12-months following implantation, and to determine the proportion of patients who experience adverse events during and after the implantation procedure, including comorbidities and overall mortality rates. The percentage of patients in whom technical and clinical success is achieved, and the percentage who experience serious adverse effects will be determined. Additional endpoints that will be evaluated are length of stay in intensive care following the procedure, total length of hospital stay and recovery time.

Patient data and follow-up information and images will be stored with the Lifeline Registry for Aneurysm Repair with periodic reports to the FDA up to the 5-year follow-up supplemented with reports from the Registry database.

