Since 1998, Harbor UCLA has treated 31 thoracic aortic lesions with the Medtronic Aneurx device, all of which have been part of commercial manufacturer DEs. A published review of 26 of these patients who were significant risks for surgical repair and who were implanted with the Aneurx thoracic stent-graft showed that 25 were treated successfully with no surgical conversions. Moreover, there was an overall decreased incidence of morbidity and mortality. (White, et al, 2001.)

An additional 14 subjects were treated with the Medtronic/Talent thoracic device and 1 Gore device between June 1998 and January 2002, either on a compassionate or emergency basis. In our experience, the Talent device has been particularly useful for patients with descending aortic aneurysms and dissections with the only limitation being adequate access for the 22 to 27 French delivery catheters.

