### **2.2.3 Withdrawal and Lost-to-Follow-up**

Patients may be withdrawn from the study for a number of reasons. The following is a summary of the possible reasons for withdrawal.

Subjects may voluntarily withdraw from the study. The reason for withdrawal must be documented on the Termination CRF (Attachment E).

After the implant procedure, some subjects may not return for follow-up visits. A minimum of three (3) attempts to contact such patients must be made. All attempts are to be documented on the Termination CRF.

Subsequent to enrollment, if new information demonstrates that a patient does not meet the inclusion/exclusion requirements, the patient must be withdrawn from the study. The reasons for withdrawal must be documented on the Termination CRF. If such information is not discovered until after the implant procedure, the patient will still be followed for safety reasons but will not be included in the final analysis.

In some cases, an implant procedure will be initiated (i.e., an attempt to pass or deploy the device) but is aborted prior to device deployment. Such patients maintain their enrollment status (since this is an intent-to-treat study) but need not

be followed. On the other hand, if a patient is initially screened and enrolled, but no procedure is ever initiated, the patient is cancelled and his/her enrollment position is made available to another patient.

Patients who are enrolled in the study group and are converted to surgery due to peri- or post-implantation complications will be followed for a minimum of 12 months after enrollment. Conversion to surgery is documented on the Procedure CRF.

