If endoleaks are detected during the implantation procedure, the stent-graft should be re-balloonned to ensure that the device has been properly modelled against the vessel wall. Endoleaks present after remodeling should be covered with an extension cuff; all other leaks that remain after remodeling may be treated with a cuff or may be monitored postoperatively, as determined by the Clinical Investigator. If patent collateral vessels are suspected of causing leaks, the vessels may be embolized at the Clinical Investigator's discretion. Endoleaks that are successfully treated during the endovascular operative procedure are not considered a complication or adverse event. Section 2.2.6, Adverse Events, has more information on treating endoleaks.

A Procedure form (Appendix E, Case Report Forms) will be completed after implantation has been accomplished. Fluoroscopy time and the amount of contrast material used will be recorded.

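### Section 2.2.4 evaluates patients who receive the device, while 2.2.3 keeps attempts aborted before deployment under intent-to-treat, so the denominator of the success and adverse-event proportions is unresolved

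*Protocol*

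**What the plan says.** Protocol 2.2.4 (Study Design) opens with "This study is a prospective evaluation of patients receiving the investigational device to determine the proportion in whom successful implantation is achieved". Success is to be judged "as indicated by aneurysm exclusion and graft patency at implant, time of discharge, and 1-, 6-, and 12-months following implantation". The same sentence goes on "to determine the proportion of patients who experience adverse events during and after the implantation procedure". The next one adds: "The percentage of patients in whom technical and clinical success is achieved, and the percentage who experience serious adverse effects will be determined". The only population named in that section is the one in the opening phrase.

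Protocol 2.2.3 (Withdrawal and Lost-to-Follow-up) deals with the case in which "an implant procedure will be initiated (i.e., an attempt to pass or deploy the device) but is aborted prior to device deployment". It then says: "Such patients maintain their enrollment status (since this is an intent-to-treat study", and adds that follow-up of these patients is not required. A patient who is enrolled but has no procedure initiated is cancelled and replaced.

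Two further places bear on the point:

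- **Procedure form.** Section 2.2.5.4.3 says: "A Procedure form (Appendix E, Case Report Forms) will be completed after implantation has been accomplished". Section 2.2.6.2 covers subjects in whom implantation cannot be completed and who are converted to surgery or observed. It puts the reason on the same form.
- **Follow-up.** Section 2.2.6.2 has those subjects followed in the same way as everyone else, with an assessment form at 1, 6 and 12 months from the attempt.

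**The concern.** A patient whose procedure is aborted before deployment has not received the device. Under 2.2.3 that patient belongs to the study population; under the literal wording of 2.2.4 the patient does not. Both sentences cannot fix the denominator, and an analyst could follow either.

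The choice matters because the abort is itself a failure of implantation. A success proportion restricted to recipients cannot register it.

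The failure is foreseeable. Section 1.1 describes earlier use of this device as useful "with the only limitation being adequate access for the 22 to 27 French delivery catheters", and 2.2.6.2 expects insertion to be difficult in some subjects.

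The primary objective in 2.1.2 is safety. Vessel rupture and blood loss, both listed in 2.2.6.4, can occur during an attempted passage. An adverse-event proportion taken over recipients would omit such events in aborted patients.

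**Working it through.** **Inputs.** The protocol plans 50 subjects (2.1.3). Because patients without an initiated procedure are replaced (2.2.3), I take N = 50 initiated procedures. Let k be the number aborted before deployment and f the number of other implantation failures. The protocol gives neither, so both are assumptions. It also states no success rate, performance goal or sample size derivation, so there is no figure of its own to reproduce.

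**Success.** The number of successes is s = 50 − k − f.

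- Over recipients: s / (50 − k)
- Over all initiated procedures: s / 50
- Gap: s/(50 − k) − s/50 = (k/50) × [s/(50 − k)]

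The gap is never negative. With f = 0 it is k/50, or 2 percentage points per abort.

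With f = 2 and exact (Clopper-Pearson) 95% intervals:

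| k | Over recipients | Over all initiated |
|---|---|---|
| 2 | 46/48 = 95.8% (85.7 to 99.5) | 46/50 = 92.0% (80.8 to 97.8) |
| 3 | 45/47 = 95.7% (85.5 to 99.5) | 45/50 = 90.0% (78.2 to 96.7) |
| 5 | 43/45 = 95.6% (84.9 to 99.5) | 43/50 = 86.0% (73.3 to 94.2) |
| 8 | 40/42 = 95.2% (83.8 to 99.4) | 40/50 = 80.0% (66.3 to 90.0) |

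With f = 0 the recipient proportion is 100% whatever k is. Over all initiated procedures it is 96.0%, 94.0%, 90.0% and 84.0% for k = 2, 3, 5 and 8.

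**Scale for k.** The only related figure is in 1.1. In a series with a different, homemade stent-graft, 103 of 108 patients had technical success, so 5/108 = 4.6% did not. Applied to 50 patients this is 50 × 5/108 = 2.3. The causes are not given, so it indicates scale only.

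**Adverse events.** Let r be the event rate in recipients and a the rate in aborted patients. The rate over all initiated procedures minus the rate over recipients is (k/50) × (a − r), so its sign depends on a. Take k = 5 and, as an assumption, 6 recipients with a serious event:

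- Over recipients: 6/45 = 13.3%
- Over all, no aborted patient with an event: 6/50 = 12.0%
- Over all, 2 of the 5 with an event: 8/50 = 16.0%

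Restricting to recipients overstates the rate in the first case and understates it in the second.

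**The case against.** The strongest reply is that 2.2.4 is a general description and defines no analysis set. Asking in what proportion implantation succeeds, starting at the implant itself, makes most sense if attempts are counted. The adverse-event clause speaks of patients and covers events during the procedure. The one explicit rule on aborted cases, in 2.2.3, keeps them. The same section says outright that patients found ineligible after implantation are left out of the final analysis, so the protocol can state an exclusion when it intends one. Analysis sets may also be set out in a statistical analysis plan that is not shown.

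Much of this stands. A reader might infer that the protocol excludes failed access from both results. The documents do not support that, because no sentence says so. Three other stronger readings also fail:

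- **That the Procedure form is confined to completed implants.** Section 2.2.5.4.3 gives a timing, and 2.2.6.2 uses the form for failed implantations. Capture is inconsistently worded, not absent.
- **That both biases favour the device.** Only the success bias has a fixed direction.
- **That access is the main failure mode to expect here.** The remark in 1.1 concerns earlier compassionate and emergency cases. In this study 2.2.1 requires an adequate access site and 2.2.2 excludes lesions that prevent delivery. Both 2.2.3 and 2.2.6.2 still plan for failures that pass screening.

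The reply does not remove the conflict. Elsewhere the protocol uses receiving the device for actual implantation (2.2.5.7 and 2.3.3), and 2.2.6.2 refers to an attempted implantation when it means attempts. The unseen plan is no answer either: the protocol names two populations, and a later document could adopt either.

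**Conclusion.** The concern holds as an unresolved conflict over the denominator. Section 2.2.4 names device recipients; 2.2.3 retains aborted attempts under intent-to-treat. On the literal wording of 2.2.4, success can only be overstated. The gap is about 2 points per abort when nothing else fails, and 3.8 points (2 aborts) or 9.6 points (5 aborts) with 2 other failures. These sizes rest on 50 initiated procedures and on assumed abort and failure counts. Five or eight aborts have no source in the protocol, and the one scale figure points to about two.

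For adverse events the conclusion is narrower: events in aborted patients could be omitted, and the net effect on the rate may go either way.

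The protocol states no performance goal that the choice could overturn. The harm is to the reported rate, and to the freedom to choose its denominator once results are known.

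**What to change.** In 2.2.4, name as the denominator all enrolled patients with an initiated procedure, using the definition of initiation already in 2.2.3. No different starting point, such as anaesthesia or cutdown, is needed, since nothing shows that definition to be wrong. State that each procedure aborted before deployment counts as a failure of successful implantation, and that its procedural events enter the adverse-event proportions. Report device recipients as a secondary set.

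Align the Procedure form wording in 2.2.5.4.3 with 2.2.6.2, so that the form is completed for every initiated procedure.

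Reconcile the follow-up statements for these patients in 2.2.3 and 2.2.6.2. An abort is known to be a failure on the day. An adverse-event proportion covering the period after the procedure, however, depends on what is collected for these patients.

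The cost is a few sentences and a Procedure form for each aborted attempt, with no additional patients or procedures. The downside is that the reported success rate may be less favourable.

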### **2.1.3 Duration of the Investigation**

Accrual of study subjects will occur over approximately 3 years with all 50 subjects to be followed according to the Lifeline Registry of Endovascular Repair protocol for the life of the patient (Please see Attach C for the protocol).

---

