#### **2.2.5.7 Final Assessment**

Subjects who have completed 12 months of follow-up will continue annual follow-up examinations for life with annual reports submitted to the Food and Drug Administration for 5 years. These follow-up visits will include a physical examination, a CT, and a plain film x-ray as defined in the Chart of Study Procedures (Appendix F). Subjects who received a Medtronic/Talent stent-graft implant and who choose to discontinue participation in the study prior to study completion will be contacted to perform a final assessment prior to study closure. The final assessment will be recorded on Post-Operative Assessment and Termination CRFs.

A Termination Case Report Form will be completed for every subject regardless of the reason for study termination. A chart may be found in Appendix F indicating the times at which procedures and tests will be performed.

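### Safety proportions in section 2.2.4 have no time horizon, so with entry over about 3 years and lifelong follow-up they move with the report date at constant true risk

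*Protocol*

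**What the plan says.** Section 2.2.4 (Study Design) gives the success result fixed assessment times: "as indicated by aneurysm exclusion and graft patency at implant, time of discharge, and 1-, 6-, and 12-months following implantation". The same sentence then gives the safety result as "the proportion of patients who experience adverse events during and after the implantation procedure", "including comorbidities and overall mortality rates". The next sentence adds that "the percentage who experience serious adverse effects will be determined". None of the three safety measures has an end point. Section 2.2.7 (Scientific Soundness and Analysis of Data) adds no horizon, person-time or time-to-event measure.

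The time structure is set elsewhere:

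- Section 2.1.3: "Accrual of study subjects will occur over approximately 3 years with all 50 subjects to be followed", and follow-up is "for the life of the patient".
- Section 2.2.4: data go to the registry "with periodic reports to the FDA up to the 5-year follow-up".
- Section 2.2.5.7: patients have "annual follow-up examinations for life with annual reports submitted to the Food and Drug Administration for 5 years".
- Section 2.2.3: a patient whose implantation is aborted before deployment stays enrolled but need not be followed. A patient converted to surgery is followed for at least 12 months.
- Section 2.2.6.2: patients who are converted or only observed are followed in the same way as the others. This does not sit easily with section 2.2.3, and the two need to be reconciled.

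Section 2.1.2 names safety as the primary objective.

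**The concern.** When patients enter over several years and each report is a snapshot, a plain proportion pools people with very different time at risk. Someone implanted a month before the report has had almost no chance to show a late endoleak, migration, rupture or death, all of which sections 2.2.6.1 and 2.2.6.4 foresee. An aborted implant that is kept in the denominator but not followed counts as event-free by default.

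The result is a percentage that drifts upward across annual reports even if the device performs identically throughout. It does not answer what the 30-day, 1-year or 5-year risk is. That matters because safety is the primary objective, and because section 2.2.6.4 hypothesizes a serious adverse event rate lower than the rate expected with surgery. Such a comparison has meaning only if both figures cover the same period.

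**Working it through.** The protocol gives 50 subjects but no event rate, precision target or power calculation, so there is no figure of its own to reproduce. The check asks how far a crude proportion moves when the true risk is held constant.

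**Inputs**
- Entry: 50 patients over 3 years (section 2.1.3), assumed uniform.
- Report times T: 1 to 5 years after first entry. This is an assumption, since the documents do not say when the 5 years of reports start.
- Late hazard h, assumed constant. Section 1.1 cites a 108-patient series with 10 deaths, 5 further late deaths (beyond 30 days) and mean follow-up of 21.8 months. Taking the 10 as early deaths leaves 98 at risk, so h = 5 / (98 × 21.8/12) = 5 / 178.0 = 0.028 per year. With all 108 in the denominator it is 0.025.
- A second value, h = 0.10 per year, is purely an assumption, used to show the range.
- No dropout.

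**Formulas**
- Follow-up of a patient entered at time a is f = T − a. Among those entered by T, f is uniform from L = max(0, T − 3) to T.
- Crude proportion at T = average of 1 − exp(−h f) = 1 − [exp(−hL) − exp(−hT)] / [h(T − L)].
- Risk by t years = 1 − exp(−h t).

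**Worked example**, h = 0.028:
- T = 1, L = 0: 1 − (1 − exp(−0.028)) / 0.028 = 1.4%.
- T = 5, L = 2: 1 − (exp(−0.056) − exp(−0.140)) / (0.028 × 3) = 9.3%.
- 12-month risk 1 − exp(−0.028) = 2.8%; 5-year risk 1 − exp(−0.140) = 13.1%.

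**Late events as a crude proportion of all patients entered**

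| Report year | Mean follow-up (years) | h = 0.028 | h = 0.10 |
|---|---|---|---|
| 1 | 0.5 | 1.4% | 4.8% |
| 2 | 1.0 | 2.7% | 9.4% |
| 3 | 1.5 | 4.1% | 13.6% |
| 4 | 2.5 | 6.7% | 21.8% |
| 5 | 3.5 | 9.3% | 29.3% |
| True 12-month risk | | 2.8% | 9.5% |
| True 5-year risk | | 13.1% | 39.3% |

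At either hazard the crude figure is about half the 12-month risk at year 1, close to it at year 2 and above it from year 3. It stays below the 5-year risk throughout these reports.

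**All deaths, early deaths included.** With early risk e = 10/108 = 9.3% and h = 0.028, the crude figure is the average of 1 − (1 − e)exp(−h f):
- Years 1 to 5: 10.5%, 11.8%, 13.0%, 15.4% and 17.7%, against a 12-month risk of 11.8% and a 5-year risk of 21.1%.
- Year 8: 24.3%, now above the 5-year risk, because nothing stops the count at 5 years.

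The early component is the same at every report; only the late component drifts.

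**The case against.** The strongest reply has four parts.

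**The estimator is inferred.** Section 2.2.4 states an aim. No section says that each report divides events to date by everyone entered, and a statistical analysis plan or the registry protocol (Attachment C), neither of which is shown, could specify something better. Visit forms at 1, 6 and 12 months and yearly would support reporting by visit. This stands in part: the choice of estimator may properly be made elsewhere. But a proportion with no horizon is what the protocol itself states, beside a success measure that does have time points, and no section shown limits it.

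**The effect is small at the only hazard the document supplies.** This stands. At year 1 the late-death shortfall against 12-month risk is 2.8% − 1.4% = 1.4 percentage points among about 17 entered patients (50/3), roughly a quarter of one patient. Sampling error in 50 patients is larger. Peri-procedural events hardly move.

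**The surgical comparison is only one sentence of hypothesis**, with no figure or test. This stands too; no planned test is shown to be invalid.

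**The direction is not fixed.** A reader might infer that the stated measure always understates late events. The documents do not support that. The figure is below the 5-year risk early on, but by year 3 it exceeds the 12-month risk, and with lifelong counting it eventually passes the 5-year risk. A reader might also infer a bias of 50%, 25% and 17% in 12-month risk at years 1, 2 and 3. Those figures arise only if events are cut at 12 months and divided by all entered patients, which is a different measure from the open-ended one in section 2.2.4.

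**Conclusion.** The point holds in a limited form. As written, the safety measures in section 2.2.4 give percentages that depend on the report date at constant true risk, and they correspond to no fixed-period risk. The defect is the missing horizon together with unequal follow-up, not a bias in one direction.

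The size is illustrative. It rests on uniform entry, a constant late hazard borrowed from a cited series of a different stent-graft, complete follow-up and reports timed from first entry. On that basis the late-death proportion rises from 1.4% to 9.3% between years 1 and 5, against a 5-year risk of 13.1%. A higher assumed hazard of 0.10 per year gives 4.8% to 29.3% against 39.3%. The point should be corrected because it concerns the primary objective and the remedy is cheap, but it does not undermine the early results.

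**What to change.** Replace the open-ended proportions in section 2.2.4 with two sets of defined results:

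1. **By day 30:** the proportions with a serious adverse event and the proportion dead, among all patients with an attempted implantation. Aborted implants stay in the denominator, and the number with unknown status is shown. Restricting the denominator to patients with complete 30-day status could drop the aborted cases.
2. **At 12 months and yearly to 5 years:** mortality by Kaplan-Meier, and late device events by cumulative incidence with death as a competing event. Censor at last contact, and give numbers at risk and confidence intervals.

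Use the same definitions in every annual report. Estimator details may sit in the statistical analysis plan, but the horizons and denominators belong in the protocol. Reconcile sections 2.2.3 and 2.2.6.2 on which patients without a completed implant are followed, since this determines whose status is known.

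The cost is a few sentences, slightly more analysis work, and wider intervals in early reports. The planned visits at 1, 6 and 12 months and yearly already fit these horizons. The case report forms are not shown, so confirm that they capture event and last-contact dates.

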## **2.2.5 Study Procedures**

### **2.2.5.1 Subject Screening and Evaluation**

Prospective subjects will be evaluated for enrollment in the study at the time they are considered to be candidates for repair of thoracic aortic lesions. Initial screening will include all diagnostic imaging tests performed as part of the patient's routine medical care. Spiral CT scan with possible angiogram is the minimum diagnostic imaging required to determine suitability for Medtronic/Talent stent-gaff implantation. Prospective subjects who meet the inclusion/exclusion criteria specified in Sections 2.2.1 and 2.2.2 will be invited to participate in the study and give written informed consent. The patient will be given two consents: one for the implantation of the device and the other one for enrollment in the Endovascular Lifeline Prosthesis Registry.

